4.3.2 Primary efficacy endpoint analysis

The estimand of the primary analysis for MDS-UPDRS Part I+II+III total score at Week 72 is the mean difference of the change from baseline at Week 72 between treatment groups in the ITT population regardless of whether start of PD medication had occurred or not. Specifically, the estimand takes the following into consideration:

- A. Population: ITT population as defined in Section 4.1.1;
- B. Variable: change from baseline to Week 72 in the MDS-UPDRS Part I+II+III total score;
- C. Intercurrent events: regardless of whether start of PD medication had occurred or not;
- D. Population-level summary: difference in variable means between each early start group and delayed start group

Change from baseline in the MDS-UPDRS Part I+II+III total score at Week 72 will be analyzed using an MMRM model for all the visits in the placebo-controlled and DBE period.

Data after subjects start PD medication will be included in the primary analyses.

For details on the model to be used please refer back to the Year 1 SAP, for the analyses of MDS-UPDRS including data after PD medication. Adjusted means for each treatment group,

CONFIDENTIAL

The information contained herein may not be used, disclosed, or published without the written consent of Biogen MA Inc.

	Statistical Analysis Plan Dose Blinded Extension Period	V2.0
---	--	-------------

pairwise adjusted differences for the comparisons, 95% confidence intervals for the differences will be presented at each visit, and p-values will be presented for the key visits of week 24, 52, and 72. Dose-response testing will be done using the adjusted mean with the pre-specified MCP-MOD procedure with pre-specified candidate models (refer to Year 1 SAP Sample Size Consideration section). If the distribution of the outcome is highly skewed, p-value will be generated from the MMRM model based on the rank data. Missing data are assumed to be missing at random behind the MMRM model.

A multiple comparison adjustment method (graphical procedure) will be applied to control the overall type I error at 0.05 in the study, due to the primary endpoint of MDS-UPDRS total score being analyzed at Week 52 and Week 72, and superiority against placebo is considered reached in study if statistically significant result is achieved at either timepoint. Please refer to the “Interim Analysis” section for this method. Pairwise comparison of each active group versus delayed-start group(s) will also be conducted, however, no additional multiplicity adjustment will be made, and nominal p-values will be reported. The primary comparison is between each of the early-start BIIB054 dose group, with the pooled delayed-start BIIB054 group.

The following three comparisons will be evaluated for the long-term efficacy analyses of BIIB054:

- The early start 250 mg compared with the pooled delayed start group;
- The early start 1250 mg compared with the pooled delayed start group;
- The early start 3500 mg compared with the pooled delayed start group

The following comparisons may also be evaluated:

- The early start 250 mg compared with the delayed start 250 mg;
- The early start 1250 mg compared with the delayed start 1250 mg.
- The early start 3500 mg compared with the delayed start 3500 mg.

Per design, a subset of subjects will enter year 3 and 4 for a limited time. There will be some visits with too few data in year 3 and 4. If this is the case, the visits with too few data will be excluded from the MMRM analyses, Otherwise, the MMRM model will not converge. In addition, since most patients will start PD medication by year 1, most data in year 2-4 will be after PD medication. Therefore, data after subject start PD medication will be included in the MMRM analyses. Otherwise, the MMRM model will not converge.

Data at the common visits of cohort A and cohort B will be included in the by visit summary and MMRM model. Data at all visits will be listed.

CONFIDENTIAL

The information contained herein may not be used, disclosed, or published without the written consent of Biogen MA Inc.

	Statistical Analysis Plan Dose Blinded Extension Period	V2.0
---	---	-------------

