5.3.2.3 Sensitivity analysis

A sensitivity analysis will be conducted for MDS-UPDRS based endpoints, by including the data after PD medication assessed in the “OFF” status, that is, the assessment was made at least 12 hours since the last time the subject took the medication, or assessed in the “off” status by the rater, or if subject reported not taking PD medication at that visit.

The analyses will be performed based on the same MMRM model as described for the primary endpoint, except the following:

- An unstructured covariance matrix will be used to model the within-subject variance-covariance errors (instead of random intercept and slope). If the unstructured covariance structure matrix results in a lack of convergence, the heterogeneous Toeplitz covariance structure followed by the heterogeneous first-order autoregressive covariance structure will be used.

[figure not shown]
The table below summarizes the detailed information.

		Primary analyses		Sensitivity analyses	
MDS-UPDRS endpoints	Type	MMRM model covariance structure	Data after PD medications included (Y/N)	MMRM model covariance structure	Data after PD medications included (Y/N)
I+II+III	Primary	Based on random slope and intercept	N	Based on pre-specified covariance structure (UN if no convergency issue occurs)	Y
I	Secondary		N		Y
II	Secondary		N		Y
III	Secondary		N		Y
██████	██████		█		█
██████	██████		█		█
██████	██████		█		█

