5.3.3 Other clinical efficacy endpoints

Other clinical efficacy (function) and quality of life assessments are listed as below. The questionnaire as well as the scoring algorithm for these clinical assessments are described in Appendix I.

- [REDACTED]
- [REDACTED]
- [REDACTED]
- [REDACTED]
- [REDACTED]
- [REDACTED]
- [REDACTED]
- [REDACTED]
- [REDACTED]
- [REDACTED]
- [REDACTED]
- [REDACTED]
- [REDACTED]
- [REDACTED]
- [REDACTED]
- Clinical Global Impressions Improvement (CGI-I) Scale (collected at Week 52 in the US sites only)*,
- Patient Global Impression of Change (PGI-C) (collected at Week 52 in the US sites only)*.

Data after PD medication will be included in the analysis for all the outcomes except [REDACTED].

For each clinical assessments that are collected longitudinally, an MMRM model will be used to analyze the change from baseline in the continuous clinical outcome, with addition of adjustment for the corresponding baseline outcome value and its interaction with time. i.e. the model will include fixed effects of treatment group (categorical), time (categorical), region (categorical), treatment group-by-time interaction, baseline value of the corresponding outcome (continuous), baseline value of the outcome by time interaction, baseline MDS-UPDRS I+II+III total score (continuous), baseline MDS-UPDRS I+II+III total score-by-time interaction, baseline striatum SBR values (continuous), and baseline striatum SBR by time interaction. The endpoints listed with a “*” next to them, will additionally include the baseline PD subtype (categorical) as a covariate. An unstructured covariance matrix will be used to model the within-subject variance-covariance errors. If the unstructured covariance structure matrix results in a lack of convergence, the heterogeneous Toeplitz covariance structure followed by the heterogeneous first-order autoregressive covariance structure will

CONFIDENTIAL

The information contained herein may not be used, disclosed, or published without the written consent of Biogen MA Inc.

be used. Least square means (LSmeans) of each treatment group as well as treatment difference between BIIB054 groups and placebo will be displayed with 95% CI and p-value at Week 52.

For CGI-I and PGI-C that are only collected at Week 52, an ANCOVA model will be used to analyze the data and adjust for the covariates of baseline MDS-UPDRS I+II+III (continuous) and baseline striatum SBR values (continuous), and baseline PD subtype (categorical).

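### The Week 72 primary MMRM falls back to covariance structures that, with model-based errors, can understate the standard error of an alpha-controlled test; the risk depends on unstructured covariance failing and on how much slopes vary

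*SAP*

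**What the plan says.** Section 4.3.2 of the dose-blinded extension (DBE) SAP says that the change in MDS-UPDRS Parts I+II+III at Week 72 "will be analyzed using an MMRM model for all the visits in the placebo-controlled and DBE period". For the model, "please refer back to the Year 1 SAP, for the analyses of MDS-UPDRS including data after PD medication". That analysis is in Year 1 SAP 5.3.2.3: "An unstructured covariance matrix will be used to model the within-subject variance-covariance errors (instead of random intercept and slope". If this does not converge, "the heterogeneous Toeplitz covariance structure followed by the heterogeneous first-order autoregressive covariance structure will be used". Everything else follows the Year 1 primary model in 5.3.2.1, including Kenward-Roger. Neither SAP names an empirical (sandwich) standard error.

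DBE SAP 4.3.2 narrows the visit set for Years 3 and 4: "the visits with too few data will be excluded from the MMRM analyses, Otherwise, the MMRM model will not converge". It does not say how few is too few. Only visits common to Cohorts A and B enter.

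The adjusted means go into MCP-MOD. Under DBE SAP 4.10 the Week 72 result is tested at 0.01, or at 0.05 if Week 52 succeeds at 0.04. Success at Week 72 returns 0.01 to Week 52.

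**The concern.** This is one of the two tests on which the overall 0.05 claim rests. Heterogeneous Toeplitz and AR(1) let the variance differ by visit but force one correlation for all pairs of visits the same number of steps apart. When subjects progress at different rates, late visits correlate more strongly than early ones. Maximum likelihood then reconciles a pooled correlation with the data partly by shrinking the fitted variance at late visits, so the model-based standard error at Week 72 is too small. Kenward-Roger allows for estimating the covariance parameters; it does not repair a wrong structure.

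The visit set adds to this. The Week 72 estimate does not need later visits, yet they enter the model and may make non-convergence more likely. The exclusion clause names only Years 3 and 4. At the Week 72 analysis, late Year 2 visits may also be partly filled, and the clause does not mention them.

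**Working it through.** **Plan's own figure.** Inputs: evaluable N of 86/46/86/86 (Table 3.4), Week 72 SD 13.7, a 55% reduction of 9.6 (5.28 points), the seven candidate models of Year 1 Appendix III, and 2-sided 0.05. The MCP-MOD maximum-contrast test then has average power 74.1%, against about 73% stated. At Week 52 it is 81.8% against about 80%. (The printed active mean of 3.84 is a 60% reduction and gives 81.2%; that is a separate matter.) The alpha split adds up: 0.04 + 0.01 = 0.05.

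**A true covariance consistent with the SAP's SDs.** Assume random intercept and slope, as in the Week 52 primary model, with intercept and slope uncorrelated and time in units of 52 weeks.
- Slope variance = (13.7² − 10.64²) / ((72/52)² − 1) = (187.69 − 113.21) / 0.917 = 81.2.
- Intercept plus residual variance = 113.21 − 81.2 = 32.0.

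**Why the fallbacks misfit.** Split the 32 as 16 intercept and 16 residual. Then Cov(s,t) = 16 + 81.2·s·t, and Var(t) = 32 + 81.2·t². Three pairs of visits, each 24 weeks apart:
- Weeks 8 and 32: 23.7 / √(33.9 × 62.8) = 0.51
- Weeks 24 and 48: 50.6 / √(49.3 × 101.2) = 0.72
- Weeks 48 and 72: 119.8 / √(101.2 × 187.7) = 0.87

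On evenly spaced visits, Toeplitz and AR(1) must give all three the same correlation.

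**Effect on the Week 72 test.** Each fallback was fitted by large-sample maximum likelihood to this covariance, with treatment-by-visit means and monotone dropout of 10% by Week 52 and 15% by Week 72. Let r be the model-based variance of the Week 72 mean divided by its sandwich variance. Then

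actual type I error = 2 × (1 − Φ(z × √r)).

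At the worst end r is about 0.66. At nominal 0.05, 1.960 × 0.812 = 1.592, giving about 0.11. At nominal 0.01, 2.576 × 0.812 = 2.093, giving 0.036. At the other end an error of 0.086 means z√r = 1.717, so r = (1.717/1.960)² = 0.77 and the 0.01 test runs at 0.024. The standard error is therefore about 12% to 19% too small (1 − √0.77 to 1 − √0.66).

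| True covariance | Nominal 0.05 | Nominal 0.01 |
|---|---|---|
| Slope variance 81.2 (Week 72 SD 13.7) | 0.086-0.110 | 0.024-0.036 |
| Same, visits only to Week 72 | 0.086-0.105 | 0.024-0.033 |
| Moderate slope variance | 0.065-0.076 | 0.015-0.020 |
| Small slope variance | 0.054-0.058 | 0.011-0.013 |
| Compound symmetry | no inflation | no inflation |
| Any, unstructured converged (r = 1) | 0.05 | 0.01 |

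Moderate is roughly half of 81.2 with the Week 52 SD held at 10.64, so the Week 72 SD is √(113.21 + 40.6 × 0.917) = 12.3. Small is roughly one fifth, with a Week 72 SD of √(113.21 + 16.2 × 0.917) = 11.3. Other assumed visit schedules and variance splits move the ranges at nominal 0.05: from 0.080 upward in the first row, 0.072-0.102 in the second, 0.067-0.086 for moderate and 0.056-0.065 for small slopes.

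**Cross-checks.** In 400 simulated trials of 357 subjects with AR(1) and visits to Week 96, the rates were 0.103 and 0.033. For the MCP-MOD maximum test, r between 0.66 and 0.84 gives 0.077-0.127 at 0.05 and 0.020-0.043 at 0.01.

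**Effect of later visits.** Adding visits to Week 96 took the AR(1) error from 0.087 to 0.110 in one scenario. Toeplitz changed little.

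**Overall error.** With no effect at either time point, the overall error is at most the sum of the two levels: 0.04 + 0.024 = 0.064 to 0.04 + 0.036 = 0.076, instead of 0.05. These are upper bounds, not estimates.

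**The case against.** Four points count on the other side.

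1. **Visit set.** A reader might infer that every extension visit enters the model and that the SAP expects unstructured covariance to fail. The document does not support this. Sparse Year 3-4 visits are to be dropped precisely to avoid non-convergence. What is missing is the threshold.

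2. **Cause.** A reader might blame the later visits for the inflation. They are not the main cause, since the fallback gives 0.086-0.105 with visits only to Week 72. Cutting the visits alone would not restore control.

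3. **Likelihood of failure.** Every inflated figure needs unstructured covariance to fail, and nothing shows that this is likely. An unstructured fit by the EM algorithm, under the large-slope assumptions with 357 subjects, converged in 60 of 60 simulated trials with visits to Week 96 and in 60 of 60 to Week 120. That fit omitted the full covariates and was not run in SAS, so it shows only that failure cannot be presumed.

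4. **Size.** A slope variance of 81.2 is 72% of the Week 52 variance (81.2/113.2). The SDs are planning values from an outside cohort. The Week 72 estimand includes scores after PD medication, for which the SAP replaces random intercept and slope with unstructured covariance, so the SAP does not adopt the structure assumed above for these data.

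All four stand as limits on the claim. The covariance order is also prespecified and triggered by convergence rather than by results, so only the visit exclusion is left to judgement. None of this removes the defect: where the fallback is reached, the plan has no protection against a wrong structure in a confirmatory test.

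**Conclusion.** The point holds as a conditional risk. If the Week 72 model leaves unstructured covariance and slopes vary as widely as the SAP's two SDs could imply, the single-contrast error is about 0.09-0.11 at nominal 0.05 and 0.024-0.036 at nominal 0.01. It is much smaller with less slope variation and absent under compound symmetry. A flat statement that the false-positive rate doubles would go too far; that is the upper end and needs both conditions.

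The figures rest on assumptions outside the documents: the visit schedule (about 8-weekly in Year 1, then Weeks 60, 72 and later), retention after Week 72, the split between intercept and residual variance, dropout completely at random, and equal covariance across arms. The Week 52 primary model uses a different structure and is not affected. The repair is cheap enough to make without settling how likely the failure is.

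**What to change.** In DBE SAP 4.3.2:

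- State that if any structure other than unstructured is used for the Week 72 primary test, the LSmeans covariance passed to MCP-MOD comes from the empirical (sandwich) estimator. This is the part that addresses the error rate. In large samples it restores the nominal level, and in 250 simulated trials with 14% missing-at-random dropout it gave rates at or below nominal (Monte Carlo error about 1.4 points at 5%).
- Fit this model only to common visits up to and including Week 72. Put later visits in a separate long-term model that does not revise the Week 72 p-value. The undefined exclusion of sparse visits then no longer touches the primary test.

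The cost is SAP wording and one program option. There are two downsides: the sandwich option replaces Kenward-Roger when it is used, and data after Week 72 from subjects who missed Week 72 are not used.

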4.3.3 Secondary efficacy endpoints and additional endpoints analysis

Secondary endpoints, e.g., change from baseline in the MDS-UPDRS subscores (e.g., Part I, II, or III score, Part II and III total score) will be analyzed in a similar model, but no additional multiplicity adjustment will be made or for other secondary endpoints.

4.3.3.1 MDS-UPDRS based endpoints

The analysis approaches and the MMRM model described will be performed for additional MDS-UPDRS based endpoints as listed below, except that, 1) the baseline MDS-UPDRS total score term in the model will be replaced by the corresponding baseline value of MDS-UPDRS total or sub-part score being analyzed, 2) MCP-MOD dose-response may be performed, 3) no additional multiple comparison adjustment will be applied for secondary efficacy and exploratory efficacy endpoints

- MDS-UPDRS Parts I, II, III (**Secondary Efficacy Endpoints**),
- MDS-UPDRS Total Score (I+II+III) at the end of the study
- MDS-UPDRS Parts II+III, Ib+II+III
- MDS-UPDRS Part IV
- Postural Instability -Gait Difficulty (PIGD) score (mean score of MDS-UPDRS items 2.12+2.13+3.10+3.11+3.12),
- Lower Extremity (LE) score (mean score of MDS-UPDRS items 3.10+3.11+3.12+3.13+3.3d+3.3e+3.7a+3.7b +3.8a+3.8b+3.17c+3.17d+2.12+2.13), and Tremor score (mean score of MDS-UPDRS items 2.10+3.15a+3.15b+3.16a+3.16b+3.17a+3.17b+3.17c+3.17d+3.17e+3.18).

4.3.3.2 Other clinical efficacy measures

[Redacted text block containing multiple lines of blacked-out content]

CONFIDENTIAL

The information contained herein may not be used, disclosed, or published without the written consent of Biogen MA Inc.

	Statistical Analysis Plan Dose Blinded Extension Period	V2.0
---	---	-------------

[REDACTED]

[REDACTED]

[REDACTED]

- [REDACTED]
- [REDACTED]
- [REDACTED]
- [REDACTED]

[REDACTED]

4.4 Pharmacodynamics analyses

There are three types of imaging outcomes in the study: DaT/SPECT imaging, [REDACTED]. Please refer to the placebo-controlled SAP for details.

The analysis population for pharmacodynamic analyses is defined in Section 3.1.1. The analysis period is placebo-controlled and DBE period combined. That is, data from both the placebo-controlled and DBE periods will be included in the analyses.

Similar analyses will be conducted for the pharmacodynamic analyses as for the clinical outcome analysis. The main comparison will be between the early and delayed-start groups. The pooled delayed start group contains all the subjects who were randomized to placebo treatment in the placebo-controlled period including those who did and who did not enter to the DBE period. There will be no multiple comparison adjustments. Data after subjects start PD symptomatic treatment will be included in the analyses.

Visit Windows for by visit analyses

CONFIDENTIAL

The information contained herein may not be used, disclosed, or published without the written consent of Biogen MA Inc.

	Statistical Analysis Plan Dose Blinded Extension Period	V2.0
---	--	-------------

For the by visit summaries and MMRM models, the analysis visit should be defined using visit windows (see Table 3 in the Appendix). If there is more than 1 value in the same analysis visit window (>1 value for the same analysis visit) for a certain parameter for a subject, then the closest record to the target visit day will be used for the by visit analysis. If they are with the same distance from the target visit day, then the record with the later time will be used for the by visit analysis.

A prespecified set of imaging measures as well as the change from baseline will be summarized by DBE treatment groups by visit for all the visits in the placebo-controlled and DBE period.

MMRM model analyses:

Similar MMRM model will be used to conduct the pharmacodynamic analyses as for the clinical outcome analysis, with the same terms included in the model.

4.5 Safety Analyses

4.5.1 General Considerations

Analysis population

Safety population will be used for safety analyses of AEs, clinical laboratory data, vital sign data, ECG data, physical and neurological examination findings, Columbia Suicide Severity Rating Scale (C-SSRS) data and MRI safety data.

DBE safety treatment groups

Please refer to Section 3.1 for the safety treatment groups. Subjects who were randomized to placebo group but accidentally received one or more doses of BIIB054 during the placebo-controlled period will be classified as early start for all the safety analyses that involves DBE, and their applicable safety data in the placebo-controlled period will be included in the analysis for active treatment (placebo-controlled and DBE) period.

Safety analysis period

Analysis period will be specified for each output. Analyses periods in this SAP are

- Long-term extension period – for AE analyses
- Active treatment (placebo-controlled and DBE) period - for AE analyses and analyses of hematology/blood chemistry/urinalysis, hepatotoxicity, vital sign, ECG, MRI.

Safety data in the specified analysis period will be included in the analysis. Listings will include all data in the placebo-controlled and DBE period, unless otherwise specified.

Incidence, incidence proportion and incidence rate

- Incidence and incidence proportion will be provided in incidence tables. Incidence is defined as the number of subjects who experienced an event. Incidence proportion is

CONFIDENTIAL

The information contained herein may not be used, disclosed, or published without the written consent of Biogen MA Inc.

	Statistical Analysis Plan Dose Blinded Extension Period	V2.0
---	--	-------------

defined as the number of subjects who experienced an event divided by the total number of subjects in the analysis population, i.e., percentage. Each subject will be counted only once within each category.

- Incidence and incidence rate will be provided in incidence rate tables. Incidence rate is defined as the number of subjects who experienced an event divided by the total follow-up time among the subjects in the analysis population (e.g., incidence rate per 100 subject-years). The total follow-up time is the sum of all subjects' follow-up time. The follow-up time for a subject is defined as the number of days (inclusive) from the first dose of treatment until the last day on study divided by 365.25. For active treatment (placebo-controlled and DBE) period analyses, the first dose of treatment is considered as the first dose received in the study period (PC or OLE) in which a subject first receives BIIB054. Each subject will be counted only once within each category.

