4.1.2 Analyses period

Depending on the purpose, different analyses will be conducted on the following study periods:

1. DBE period. Only data in the DBE period will be included in these analyses. For example, incidence table of adverse events in the DBE period.
2. Placebo-controlled and DBE period. All the data in the placebo-controlled and DBE periods will be included in these analyses. For example, mean plot of actual laboratory values in the placebo-controlled and DBE period.

CONFIDENTIAL

The information contained herein may not be used, disclosed, or published without the written consent of Biogen MA Inc.

	Statistical Analysis Plan Dose Blinded Extension Period	V2.0
---	--	-------------

3. Active treatment (placebo-controlled and DBE) period (i.e., Total BIIB054 experience) period. Active treatment period is defined as the study period(s) that a subject is assigned to BIIB054. For early start subjects – subjects who are assigned to BIIB054 in both placebo-controlled and DBE period, all the data (placebo-controlled and DBE periods) will be included in the analyses. For delayed start subjects – subjects who are assigned to placebo in Year 1 and BIIB054 in the DBE period, only data in the DBE period will be included. For example, incidence table of adverse events in the active treatment (placebo-controlled and DBE) period will not include the AEs started on placebo treatment in year 1.

Subjects to be included in a certain output is determined by both the analysis population and the analysis period. For example, the incidence table of adverse events in the DBE period will include subjects in the safety population for the DBE period, i.e., all randomized subjects who received at least one dose of study treatment in the DBE period. The incidence table of adverse events in the active treatment (placebo-controlled and DBE) period will include subjects in the safety population for the active treatment period, i.e., all randomized subjects who received at least one dose of study treatment in the active treatment period. In this SAP we do not separately define the analysis population in each analysis period.

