4.5.2.2 **Incidence and incidence rate analysis for active treatment (placebo-controlled and DBE) period**

Due to the different length of active treatment (placebo-controlled and DBE) period in early start versus delayed start subjects, both incidence (proportion) tables and incidence rate tables will be used for AE analyses in this period. The entire follow-up time is from the first dose in

CONFIDENTIAL

The information contained herein may not be used, disclosed, or published without the written consent of Biogen MA Inc.

	Statistical Analysis Plan Dose Blinded Extension Period	V2.0
---	--	-------------

active treatment period (first dose in placebo-controlled period for early start subjects and first dose in DBE period for delayed start subjects) until the last day in the study.

The following incidence (proportion) will be provided for the active treatment (placebo-controlled and DBE) period. The follow-up adjusted incidence rate table will be provided for 1, 10, 12, 14, 16 and 17.

1. AEs by system organ class and preferred term sorted by decreasing frequency
2. AEs by system organ class and preferred term sorted by alphabetical order analysis
3. AEs by system organ class
4. AEs by preferred term
5. AEs with an incidence of 5% or more in any treatment group by preferred term
6. Severe AEs by system organ class and preferred term
7. Severe AEs by preferred term
8. AEs by maximum severity by system organ class and preferred term (System organ class will be presented alphabetically. Preferred term will be presented in decreasing frequency order).
9. AEs by maximum severity by preferred term (Preferred term will be presented in decreasing frequency order)
10. Study drug related AEs by system organ class and preferred term
11. Radioligand related AEs by system organ class and preferred term
12. SAEs by system organ class and preferred term
13. SAEs by preferred term
14. Study drug related SAEs by system organ class and preferred term
15. Radioligand related SAEs by system organ class and preferred term
16. AEs that led to discontinuation of study treatment by system organ class and preferred term
17. AEs that led to withdrawal from study by system organ class and preferred term
18. AEs that occurred within 2 hours from infusion start by system organ class and preferred term

The following listings will be provided for the placebo-controlled and DBE period:

1. Listing of AEs
2. Listing of SAEs

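### The active-treatment-period adverse-event incidence rate counts first events but divides by full follow-up, so it adjusts only imperfectly for unequal exposure when events are frequent

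*SAP*

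**What the plan says.** The definition is in the SAP for the dose-blinded extension (DBE), Section 4.5.1, under incidence, incidence proportion and incidence rate: "Incidence rate is defined as the number of subjects who experienced an event divided by the total follow-up time among the subjects". A subject's follow-up is the number of days "from the first dose of treatment until the last day on study divided by 365.25". The counting rule is "Each subject will be counted only once within each category".

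Section 4.5.2.2 gives the reason for having rates as well as proportions: "Due to the different length of active treatment (placebo-controlled and DBE) period in early start versus delayed start subjects". It repeats that follow-up begins at the first active-period dose ("first dose in placebo-controlled period for early start subjects and first dose in DBE period for delayed start subjects") and ends on the last day in the study. It then names the outputs: "The follow-up adjusted incidence rate table will be provided for 1, 10, 12, 14, 16 and 17". These items are all adverse events (AEs), drug-related AEs, serious AEs (SAEs), drug-related SAEs, AEs leading to treatment discontinuation and AEs leading to study withdrawal, each by system organ class and preferred term.

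Nowhere does the SAP stop a subject's clock at the first event, and it defines no rate that counts all episodes.

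**The concern.** The numerator can rise by at most one per subject and category. The denominator keeps growing after that subject has had the event and can add nothing more to the numerator. The ratio therefore depends on how long subjects are followed, even when the underlying hazard is constant.

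Follow-up length is exactly what differs between the two groups. Section 4.1.2 limits delayed-start subjects to extension data in this analysis period, while early-start subjects contribute Year 1 as well. Section 4.1 sets the early- and delayed-start columns side by side in the safety outputs. A reader of a follow-up adjusted table will assume that the difference in exposure has been removed. For frequent events it has been replaced in part by an artefact in the other direction.

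**Working it through.** **The plan's own figures.** The SAP states no AE rate, so there is none to reproduce. Its only AE figures, in Section 3 with 100 subjects per arm, are detection probabilities, and both check: 1 − 0.984^100 = 0.801 (stated 80%) and 1 − 0.977^100 = 0.902 (stated 90%).

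**Follow-up, from Section 2.1.2.**
- Minimum: dosing through Week 96 plus a final visit 12 weeks later gives Week 108. Early start: 108 × 7 / 365.25 = 2.07 years. Delayed start, from Week 52: 56 × 7 / 365.25 = 1.07 years.
- Maximum: 16 further four-weekly doses put the last dose at Week 160. Assuming the same 12 weeks afterwards, the end is Week 172. Early start: 3.30 years. Delayed start: 120 weeks, 2.30 years.

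**Assumption.** The hazard of a first event, h, is not in the documents. It is taken as constant and equal in both groups, over a range of values.

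**Formulas.** With follow-up T, the proportion with an event is 1 − exp(−hT).
- Rate as written: (1 − exp(−hT)) / T, which falls as T rises.
- Rate on time at risk: the mean time to first event or end of follow-up is (1 − exp(−hT)) / h, so the rate is h for any T.

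Example at h = 0.5: early 0.645 / 2.07 = 31.2 and delayed 0.415 / 1.073 = 38.7 per 100 subject-years, ratio 0.805. On time at risk both are 50.0.

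| Assumed h per year | Early, as written | Delayed, as written | Ratio, minimum follow-up | Ratio, maximum follow-up | Ratio on time at risk |
|---|---|---|---|---|---|
| 0.05 | 4.75 | 4.87 | 0.976 | 0.976 | 1.000 |
| 0.2 | 16.4 | 18.0 | 0.910 | 0.914 | 1.000 |
| 0.5 | 31.2 | 38.7 | 0.805 | 0.825 | 1.000 |
| 1.0 | 42.2 | 61.3 | 0.688 | 0.747 | 1.000 |

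Rates are per 100 subject-years at minimum follow-up.

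**Dropout.** In a simulation with an assumed 10% dropout per year at minimum follow-up, the ratio is 0.92, 0.82 and 0.71 at h = 0.2, 0.5 and 1.0.

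**Hazards that change over time.** Weibull hazards were run with shape 0.5 to 2 and one-year cumulative hazard 0.05 to 1. The ratio as written was below the time-at-risk ratio in every case, but the ordering of the groups is not fixed. At cumulative hazard 0.5, the ratios as written and on time at risk were 0.66 and 0.75 for shape 0.5 (falling hazard), 0.94 and 1.26 for shape 1.5, and 1.05 and 1.50 for shape 2 (rising hazard).

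**Comparison with the unadjusted proportion.** The proportion ratio is the rate ratio times 108/56 = 1.929. That gives 1.88, 1.75, 1.55 and 1.33 at the four hazards. On a ratio scale, the rate is further from 1 than the proportion only when its ratio is below 1/√1.929 = 0.72, which happens at a hazard between 0.5 and 1.0 per year.

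**The case against.** The strongest reply is that the rate does most of its job where most of the rows are. At 0.05 per year it turns a proportion ratio of 1.88 into 0.98, and it beats the proportion until events become very common. That stands: the adjustment is imperfect, but it has not failed.

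Second, the table is descriptive. Section 4.1 names efficacy endpoints for statistical testing, and no test, interval or decision rule uses this rate. That also stands.

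Third, a reader might infer that a real excess would be hidden. Within the rate table alone there is something in this. At a delayed-start hazard of 0.5 per year, an early-start hazard 1.56 times as high would give equal rates. At 1.0 per year no excess could show, because the early rate cannot exceed 1/2.07 = 48 per 100 subject-years against 61. The documents do not support extending this to the safety assessment as a whole:
- Section 4.5.2.2 also gives proportions, which err the other way.
- Section 4.5.2.1 gives AE tables for the extension alone ("Only data in the DBE period will be included", Section 4.1.2), where both groups are observed from Week 52.
- The Year 1 SAP compares AEs with placebo over equal planned follow-up (Section 5.4.2).
- All AEs are listed.

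Fourth, a reader might infer that a headline rate for any AE is distorted. The SAP does not say that the rate tables carry such a row, and the overall summary in Section 4.5.2.1 reports numbers of subjects.

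None of this answers the core point. The denominator does not match the numerator, and the rate still depends on the follow-up length it was introduced to handle.

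**Conclusion.** The definition is wrong as written and should be fixed; it is not a defect that by itself puts the safety conclusions at risk. With equal, roughly constant hazards and about one year more active follow-up, the early-start group shows a lower rate than the delayed-start group.

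The size depends on event frequency, which is assumed because the documents give none. The distortion is under 3% at or below 5 events per 100 subject-years, about 9% at 20, about 20% at 50 and about 31% at 100. It is therefore negligible for rare preferred terms and most SAEs. It should also be small for withdrawals due to AEs (item 17), where follow-up ends close to the event. It is material mainly for frequent system-organ-class and preferred-term rows in item 1, and in item 10 if drug-related AEs turn out to be common.

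The statement that early-start rates always look falsely lower would go too far. With a rising hazard the early-start rate can be the higher one, and with a falling hazard part of a low ratio is genuine.

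**What to change.** In DBE SAP Sections 4.5.1 and 4.5.2.2, define time at risk separately for each event category: from the first active-period dose to the first event in that category, or to the end of follow-up if there is none. Compute the rate as subjects with the event divided by total time at risk, and apply it to items 1, 10, 12, 14, 16 and 17. For item 17 the change will make little difference, but one definition for all six is simpler.

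The cost is one sentence and a small programming change, using AE onset dates that are already collected. The Year 1 SAP (Section 5.4.2) already imputes partial onset dates for its listings, and that rule could be carried over.

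The change removes the denominator artefact only. Early- and delayed-start exposure would still differ in calendar time and disease stage, and a hazard that truly changes over time would still produce different rates. A table footnote should say so.
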